Remote Ischemic Conditioning (RIC) to Decrease Postoperative Complications After Major Abdominal Surgery - A Phase IIa Trial

NCT03234543

09/08/2017

I. STUDY TITLE: Remote Ischemic Conditioning (RIC) to Decrease Postoperative Complications After Major Abdominal Surgery - A Phase IIa Trial

II: STUDY GOALS AND OBJECTIVES:

1. To obtain preliminary data regarding postoperative complications in subjects undergoing abdominal surgery and receiving remote limb ischemic or sham conditioning.

Subjects undergoing abdominal surgery will be prospectively randomized in equal proportions to receive either remote or sham lower limb ischemic conditioning immediately before surgery commences and on postoperative days 1 and 2. Each intervention will comprise 3 cycles of 5/5 minutes of inflation/deflation of a pneumatic cuff on mid-thigh. Postoperative complications within 30 days after surgery will be evaluated using Comprehensive Complication Index (CCI)¹, a continuous, scaled (0-100) and a validated measure of the total complications burden.

The preliminary data is expected to help in determining whether larger trials of RIC to decrease postoperative complications should be pursued, and provide more reliable estimates of CCI without and with RIC, sample sizes and power in design of larger trials.

2. To test whether remote limb ischemic conditioning (RIC) decreases systemic inflammatory response in patients undergoing major abdominal surgery.

Time-dependent differences between the two groups in plasma levels of inflammatory cytokines (TNF-a, IL - 1β , 6, 8 and 10), acute phase proteins (C reactive protein [CRP], alpha-1-acid glycoprotein, fibrinogen [FGN], and haptoglobin) complement components (C2, C4b, C5, C5a, and C5b-9), and blood leukocyte gene expression at baseline and one hour after completion of surgery and the second and third interventions will be tested for significance. It is hypothesized that RIC would decrease systemic inflammatory response to major surgery.

III: BACKGROUND:

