## II.2 Secondary enpoints

a) Length of hospital stay: number of days from surgery to discharge from hospital

b) 30-day mortality: (% subjects dying within 30 days)

c) Cytokine response: plasma levels (pg/mL) of TNF-a, IL - 1 $\beta$ , 6, 8 and 10

d) Acute phase response: Plasma levels of C-reactive protein (CRP),  $\alpha$ -1 acid glycoprotein, fibrinogen and haptoglobin (mg/dL)

e) Complement activation: Plasma levels of C2, C4b, C5a and C5b-9 (mg/dL)

f) Leukocyte gene expression: Global gene expression changes in peripheral blood leukocytes

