### V.2 Secondary endpoints

For endpoints that are continuous variables and are not normally distributed log transformation will be explored to achieve normality. Length of hospital stay will be compared with either a t test or Mann-Whitney test. Counts and proportions experiencing 30- day mortality will be reported. No formal intergroup comparison will be conducted regarding hospital stay and 30-day mortality.

The analyses to address the effects of RIC on plasma cytokines, acute phase response, complement activation and leukocyte gene expression will be considered independent of each other. Although these groups of outcomes are interconnected as a global innate immune responses to surgery or other injury it is quite likely that RIC may only modulate one or more rather than all the measured outcome subgroups. Furthermore, it is quite likely that RIC may modulate only one or few of the analytes in a particular subgroup

Repeated measures of continuous variables of inflammation, acute phase response and complement activation in two independent groups will be analyzed with mixed analyses of variance (ANOVA) to examined for interaction between treatment and time. If the omnibus p value is significant then additional post hoc tests will be conducted in appropriate groups. Because of the pilot nature of the study no adjustments will be made to the p values in the post hoc tests. P values <0.05 will be considered significant.

Leukocyte gene expression will be examined using RNA sequencing. Five to ten replicates in each group will be examined at baseline and postoperative day 2. A sequencing depth of 10 million reads will be utilized. Differential gene expression analyses will be performed. For individual genes with a relatively higher levels of expression relative fold changes of  $\geq$  2.0, and or p values of < 0.01 will be considered significant.

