#### VI.2 Multiple comparisons

Multiple comparisons will be performed only in the laboratory endpoints of inflammation, acute phase response and complement activation. P values for individual analytes will be reported. Due to the pilot nature of the study no adjustments to p values to accommodate multiple comparisons will be made.

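### The RNA-seq significance rule leaves open whether one or both criteria must hold, sets no numeric expression cutoff and states no false-discovery control (minor, secondary molecular endpoint)

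*SAP*

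**What the plan says.** SAP II.2(f) defines the endpoint as "Global gene expression changes in peripheral blood leukocytes". SAP V.2 sets the size of the analysis: "Five to ten replicates in each group will be examined at baseline and postoperative day 2". I read replicates as subjects.

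The decision rule closes the same section. It opens "For individual genes with a relatively higher levels of expression relative fold changes of" at least 2.0, and ends "and or p values of < 0.01 will be considered significant". No count or expression level defines the filter. No differential-expression method is named, and the p value is not said to be raw or adjusted.

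On multiplicity, SAP VI.2 states: "Multiple comparisons will be performed only in the laboratory endpoints of inflammation, acute phase response and complement activation". It then adds: "Due to the pilot nature of the study no adjustments to p values to accommodate multiple comparisons will be made". Leukocyte gene expression is not in that list, and no false-discovery control for genes appears in the protocol or the SAP.

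The contrast of interest is clear at the level of the objective. Protocol II, Objective 2, begins "Time-dependent differences between the two groups in plasma levels of inflammatory cytokines" and includes leukocyte gene expression among the measures to be tested. Only the model is unstated.

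**The concern.** The rule decides which genes are reported as significant, and three parts of it are open.

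- **The connector.** Requiring both conditions and requiring either one give very different lists. If either suffices, a two-fold difference in a handful of subjects counts with no supporting test.
- **The filter.** Without a numeric cutoff the number of genes tested is not fixed, so a reader cannot work out how many calls chance alone would produce.
- **The p value.** A per-gene threshold of 0.01 over a global screen is expected to yield a list of genes even if RIC does nothing, unless some false-discovery control is applied.

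As written, the first two choices could be made after the data are seen. At stake is the molecular reading of the trial: Protocol X.2 hopes that the study will help show the pathways through which RIC acts.

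**Working it through.** The documents give no error rate, gene count or power for this analysis, so there is no stated figure to reproduce.

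**Inputs from SAP V.2.** Fold change of at least 2.0, which is an absolute log2 difference of at least 1 if applied in both directions; p<0.01; 5 to 10 per group.

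**Assumptions, not in the documents.** 5,000 to 20,000 genes tested; SD of the per-subject log2 change of 0.5, 0.7 or 0.9; gene-wise t tests with calibrated, unadjusted p; a filter applied without reference to arm.

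**Step 1: bounds for a gene with no true effect.**
- Either condition: P(FC or p<0.01) ≥ P(p<0.01) = 1%.
- Both conditions: P(FC and p<0.01) ≤ P(p<0.01) = 1%.

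Neither bound depends on the number of genes or the SD.

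**Step 2: counts when no gene is truly changed.** Expected calls from p<0.01 alone are 0.01 × m: 50 at m = 5,000, 100 at 10,000 and 200 at 20,000.

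**Step 3: what the fold-change condition adds.** For a null gene, P(|difference| ≥ 1) = 2·P(Z > 1/(SD·√(2/n))). At n = 5 and SD 0.7 this is 2·P(Z > 2.26) = 2.39% (2.38% by simulation). At n = 10 and SD 0.9 it is 2·P(Z > 2.48) = 1.30% (1.30% by simulation). Simulating 2,000,000 null genes per setting gave these shares called significant:

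| Per group | SD | Either suffices | Both required |
|---|---|---|---|
| 5 | 0.5 | 1.1% | 0.1% |
| 5 | 0.7 | 2.8% | 0.6% |
| 5 | 0.9 | 8.0% | 0.9% |
| 10 | 0.5 | 1.0% | <0.01% |
| 10 | 0.7 | 1.0% | 0.1% |
| 10 | 0.9 | 1.7% | 0.6% |

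Check by P(either) = P(FC) + P(p<0.01) − P(both): at n = 5 and SD 0.7, 2.39% + 1.0% − 0.6% = 2.8%.

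**Step 4: false share of the resulting list, for one assumed case.** Suppose 500 of 10,000 genes truly change two-fold, with n = 5 and SD 0.7.
- Either condition: false calls 0.028 × 9,500 = 266; true calls 0.51 × 500 = 255; false share 266/521 = 51%.
- Both conditions: false calls 0.006 × 9,500 = 57; true calls 0.21 × 500 = 105; false share 57/162 = 35% (34% by simulation, from unrounded rates).

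Across SD 0.5/0.7/0.9 the simulated false shares are 25%/51%/75% (either) and 5%/34%/57% (both) at 5 per group. At 10 per group they are 17%/23%/38% and 0%/5%/25%.

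**The case against.** The strongest defence is that this is a declared pilot with a declared position. The second sentence quoted from SAP VI.2 is general and can be read as covering the whole study. The gene threshold of 0.01 is also tighter than the 0.05 used for the plasma analytes. That much stands: a reader might infer that the gene screen falls under no policy at all, and the text does not force that reading. But if the sentence is study-wide, unadjusted p becomes the plan rather than one possibility. The sentence before it would still confine multiple comparisons to three plasma families while SAP II.2 defines a global gene endpoint. Neither sentence settles the connector or the filter.

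Other limits stand as well.

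- A reader might infer that there is no expression filter. There is one, in words; what is missing is the number.
- The connector may be an and/or whose slash was lost. It would then ordinarily mean that either condition suffices. That weakens the charge of ambiguity but points to the reading with more false calls.
- A reader might infer that the two-fold criterion is itself a mistake. The documents do not support that. Required together with p, it lowers the null call rate; the problem arises only when it can stand alone.
- If both conditions are required and 10 subjects per group are sequenced, the null rate is 0.6% or less under the assumed SDs, and the problem is much smaller.

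**Conclusion.** The concern holds as a minor point about a secondary molecular endpoint. The rule is open on its connector, its numeric filter and the adjustment of p, and SAP VI.2 omits the largest testing family. With either condition sufficient and p unadjusted, about 1% of null genes tested is the floor. At 5 per group the rate is about 1% to 8% over the assumed SDs. With both conditions required, about 1% is the ceiling.

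The bounds rest on calibrated p values and a filter blind to arm. The counts rest on the assumed number of genes, and the higher rates on the assumed SDs.

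A reader might take 1% as the false share of the reported list. It is not: it is the share of unaffected genes that are called. The false share depends on how many genes truly change and by how much, which the documents do not give. Nor do the documents support carrying the point over to the CCI or to the decision on larger trials.

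**What to change.** Replace the last sentence of the RNA-seq paragraph in SAP V.2 with:

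> Genes passing a numeric low-count filter, fixed before unmasking and applied without reference to arm, will be tested for the between-arm difference in change from baseline to postoperative day 2, paired by subject. The number of genes tested and Benjamini-Hochberg adjusted p values will be reported. Only genes with an adjusted p value below 0.10 will be called significant. Genes with unadjusted p<0.01 will be listed as an exploratory ranking, with the number expected by chance (1% of genes tested). Fold change will be reported beside each gene; a two-fold change without a supporting p value will not count as significant.

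Add leukocyte gene expression to SAP VI.2. The sponsor has to supply the filter value and name the differential-expression method. Whether to keep a fold change of at least 2.0 as an additional requirement is also the sponsor's choice.

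**Cost.** Wording only, with no new samples or assays. The price is a shorter list. With 500 of 10,000 genes truly changed two-fold and SD 0.5/0.7/0.9, a 10% false discovery rate finds 8.4%/0.3%/0.1% of them at 5 per group and 88%/39%/8% at 10 per group. The present rule, with either condition sufficient, finds 60%/51%/50% and 93%/65%/52%, with the false shares shown in the working. Detection depends heavily on the size of the true change: at 5 per group and SD 0.5, a 5% rate finds about 1.5% of two-fold genes but about 54% of 2.8-fold genes. Few or no genes may therefore be called significant at 5 per group, which is why the exploratory ranking is kept.

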#### V.3 Feasibility/acceptability endpoints

The number of subjects meeting defined endpoints in each of the two study groups will be reported. No formal comparisons are proposed.

## V.4 Safety endpoints

The number of subjects experiencing each of the safety endpoints will be reported separately for the two groups. No formal comparisons are proposed.

# VI. Other considerations

#### VI.1 Missing data

**Endpoints:** The number of subjects in whom data would be missing is expected to be low due to the prospective nature of the study. The pattern of missing data will be described. Subjects with data missing for a particular outcome would be excluded from that analysis. Additional decisions about handling missing data would be made prior to any intergroup comparisons are performed.

**Baseline values of continuous endpoints**: Subjects in whom a baseline value of a continuous variable such as the laboratory analytes is missing will be included in the analyses of that outcome. A missing indicator approach, a valid method for prerandomization measures will be used.

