A prospective, randomized, double – masked clinical trial of RIC will be conducted in adult patients undergoing major abdominal surgery at University Hospital (UH) in Newark, NJ. Participants will be randomized into two groups: RIC and No RIC. In the RIC group, RIC will be induced at three time points – the first after anesthesia induction but before commencement of surgery, and the second and the third on post-operative days 1 and 2, respectively. The RIC intervention consists of 5 minutes of inflation of a pneumatic tourniquet placed mid-thigh followed by 5 minutes of deflation, repeated for 3 cycles. The pressure used will be 250 mmHg for the pre-operative intervention (a high pressure chosen because of significant variability of patient blood pressures in a recently anesthetized patient). Tourniquet pressures in postoperative interventions will be 50 mmHg above the patient's systolic blood pressure (the blood pressure is expected to be less labile than immediately after anesthesia induction). The No RIC group will receive a sham intervention at time points identical to those in the RIC group. The thigh tourniquet will be inflated to only 20 mmHg (to mask the intervention from the subject). Persistence of arterial flow will be confirmed with Doppler interrogation.

VI. STUDY POPULATION:

Adults (\geq 18 years of age) of both sexes scheduled for elective major abdominal surgery at UH are eligible for inclusion. Major abdominal surgery is defined as surgery expected to last \geq 120 minutes (from incision to closure) with an expected hospital stay \geq 2 days. A list of surgeries considered for inclusion is included as Appendix A. Additional operations will be considered for inclusion if the study team and primary surgical team both agree that the procedure is a major abdominal surgery and that the duration of surgery is likely to be \geq 2 hours.

Inclusion criteria

- 1. Adults (> 18 years of age)
- 2. Both genders

- 3. Undergoing major abdominal surgery as above
- 4. Elective surgeries
- 5. Both outpatients and in-hospital patients
- 6. Post-op length of stay expected to be at least 2 days by the primary surgical service

Exclusion Criteria

- 1. Subjects with lower extremity paralysis
- 2. Lower extremity amputees
- 3. Known, documented peripheral arterial disease
- 4. Body mass index > 45
- 5. Pregnancy
- 6. Trauma patients
- 7. Organ transplant recipients

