Subjects will be masked from recognizing which group they are in in the following manner: a) Subjects will not be informed of the group assignment throughout their participation in the study; b) subjects randomized to No RIPC will have a tourniquet placed on the thigh and inflated. It is anticipated that the subject is likely to perceive the inflation as the true RIPC. No information will be provided to subjects regarding the amount of pressure used to inflate the tourniquet in either group.

VII.4 RIC Intervention and Perioperative Care: Sham and RIC interventions will be as described above in section V. All other aspects of anesthesia care will be as per standards of practice. All aspects of the surgical procedure and postoperative care including decisions regarding discharge will be as per standards of practice. The diagnosis and treatment of complications will be under the purview of the clinical care team. The research team will not participate in the clinical care of the subjects.

VII.5 Blood Sample Collection and Processing: Ten mL of venous blood (10mL) will be collected at baseline, an hour after completion of skin closure, and an hour after completion of second and third RIC interventions. 2.5 mL will be placed in PAXgene Blood RNA tubes (Qiagen) for RNA isolation from leukocytes. RNA will be submitted to our Molecular Resource Facility for RNA sequencing. Remaining blood will be placed in EDTA tubes, centrifuged at 3500 rpm and plasma will be stored in aliquots at -70^oC.

VIII. Outcomes:

VIII.1 Primary Outcome:

The CCI, a validated and scaled score of all surgical complications (range 0 [no complications] to 100 [death]) is the primary outcome.

All complications within 30 days after surgery will be graded as per Clavien-Dindo classification.^{1,2} CCI will be computed for each subject using the publically available website, http://www.assessurgery.com/. Follow up after discharge will occur either in clinic or via telephone

VIII.2 Secondary Clinical Outcomes:

- 1. Proportion of patients in each group that complete all three RIC interventions
- 2. Hospital days

3. 30-day mortality (will be captured as part of CCI)

VIII.3 Secondary Molecular Outcomes:

- 1. Plasma cytokines levels (TNF-a, IL 1β , 6, 8 and 10)
- 2. Plasma acute phase reactant proteins (CRP, alpha-1- acid glycoprotein, FGN, and haptoglobin)
- 3. Plasma complement levels (C2, C4b, C5, C5a, and C5b-9)

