# II. Study endpoints

II.1 Primary endpoint: 30 days postoperative complications

**II.1.a** The total complications burden up to 30 days after surgery will be evaluated with the use of comprehensive complications index (CCI, [range 0-100]).

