#### II.3 Feasibility/Acceptability endpoints

Feasibility: proportions of subjects completing all 3 assigned research interventions, not withdrawing participation and completing follow up after enrollment.

Acceptability: proportions of subjects not declining any of the 3 planned research interventions

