## III. Analyses populations

**III.1** The primary analyses for efficacy will be conducted in an "**intent to treat (ITT) population** " that would include all randomized subjects.

**III.2** Additional secondary analyses for efficacy will be conducted in "**per protocol (PP) population**" that would include only subjects that completed all three interventions and follow up.

**III.3** The **Safety population** for analyses of safety endpoints will include all subjects that received at least one of the assigned interventions.

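### Does excluding subjects with a missing outcome undermine the intention-to-treat analysis of the 30-day complication index?

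*SAP*

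**What the plan says.** The primary endpoint is the CCI. In SAP II.1, "The total complications burden up to 30 days after surgery will be evaluated" with this index. SAP III.1 sets the primary efficacy analysis in an intention-to-treat population "that would include all randomized subjects". SAP VI.1 then gives the rule for absent outcomes: "Subjects with data missing for a particular outcome would be excluded from that analysis". The same paragraph expects few missing values, promises a description of their pattern, and leaves further decisions to a point before the groups are compared. The missing-indicator method in VI.1 covers baseline values only.

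On scoring, Protocol VIII.1 says "CCI will be computed for each subject using the publically available website", with death at the top of the scale. On ascertainment it says "Follow up after discharge will occur either in clinic or via telephone". Eligibility in Protocol VI requires "Post-op length of stay expected to be at least 2 days by the primary surgical service".

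The plan foresees incomplete follow-up. Feasibility in SAP II.3 includes "not withdrawing participation and completing follow up after enrollment", and under SAP V.3, "The number of subjects meeting defined endpoints in each of the two study groups will be reported". SAP III.2 adds a secondary per-protocol analysis of subjects who completed all three interventions and follow-up.

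**The concern.** Read together, III.1 and VI.1 make the primary comparison an available-case analysis by assigned group under an intention-to-treat name. The index also accumulates over 30 days, much of which may fall after discharge, so a subject can have a partial record. Two readings are open for someone discharged and then not reached:

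- the CCI is missing, and known in-hospital complications are discarded; or
- the CCI is scored on what was recorded, and later events are missed.

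Two analysts could follow the SAP and report different primary results from the same data. No sensitivity analysis for missing outcomes is named, and the per-protocol set cannot serve as one because it also requires completed follow-up. Protocol II says the trial should give more reliable CCI estimates for the design of larger trials. A biased arm mean would carry into that design even if the group difference were unharmed.

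**Working it through.** The plan gives no sample size, loss rate, CCI mean or standard deviation, so it has no figure to reproduce. Only the first step below uses document figures alone; the rest rests on stated assumptions.

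**1. Time after discharge.** Days after discharge = 30 − stay. The minimum expected stay of 2 days gives 28 of 30 (93%). Assumed stays of 7 and 14 days give 23 of 30 (77%) and 16 of 30 (53%). These are days covered by clinic or telephone follow-up. They are not missing data.

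**2. Exclusion.** Let m be the share lost, R the retained mean and T the true mean of those lost. The error in an arm's mean is m(R − T).

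- Smallest assumed case: 0.05 × 5 = 0.25 points.
- Largest assumed case: 0.15 × 20 = 3.0 points.
- Either sign is possible.

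If m and R − T are the same in both arms, the group difference is unaffected. With 5% v 15% lost and the same gap, the net shift is 0.10 × 5, 10 or 20 = 0.5, 1.0 or 2.0 points.

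**3. Recorded-only scoring.** Let r be the recorded mean of those lost. The error is −m(T − r), always downward if an added complication never lowers the index. With 2 to 10 points unrecorded, the fall is 0.05 × 2 = 0.1 to 0.15 × 10 = 1.5 points. With 5% v 15% lost and 2, 5 or 10 points unrecorded, the net shift is 0.2, 0.5 or 1.0.

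**4. The two rules compared**, at m = 10% and R = 10:

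| T | r | Exclusion | Recorded-only |
|---|---|---|---|
| 20 | 15 | −1.0 | −0.5 |
| 30 | 15 | −2.0 | −1.5 |
| 5 | 4 | +0.5 | −0.1 |
| 10 | 7 | 0 | −0.3 |

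Recorded-only scoring is closer when T − r is smaller than the absolute value of T − R. The documents cannot show whether that holds. In the last row, where loss is unrelated to the index, exclusion is unbiased and the alternative is not.

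**5. Best/worst-case bounds.** With the recorded score as floor and 100 as ceiling, the width for the group difference is 2 × m × (100 − r). With r = 10 this is 3.6, 9.0 or 18.0 points for 2%, 5% or 10% incomplete per arm. The bounds are tight only when loss is low, which is when the question hardly matters.

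**The case for a change.** The best argument for a change is that the deferral in VI.1 names no method and does not say that the decision will be made masked to arm. Low missingness is asserted only because the study is prospective, while the plan itself counts withdrawal and completion of follow-up. Equal loss should not be assumed either: Protocol V gives the arms different postoperative cuff pressures (50 mmHg above systolic v 20 mmHg), and Protocol X.1 lets subjects stop the intervention for pain. A few sentences would remove the ambiguity.

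Part of this stands. The scoring rule is unwritten, and writing it down would be tidy. The argument for differential loss is weak: stopping a session is not loss to follow-up, and Protocol VII.3 masks subjects and outcome assessors.

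The candidate remedies are also no clear improvement. Making recorded-only scoring primary exchanges an error of unknown sign for a systematic under-count. If inclusion required a complication record, lost subjects with no complications could be dropped, which selects on the outcome. Restating death as 100 repeats Protocol VIII.1. The status of a subject who dies after the third session but before day 30 is undefined in the per-protocol set, but that set is already secondary.

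**Conclusion.** No change to the plan follows. III.1 says who is analysed and in which group; VI.1 says openly what happens when the outcome is absent. That combination is common and does not mislead a reader who has both sections. What remains is one unwritten convention for subjects discharged and not reached by day 30. Analysts can settle it sensibly at the point VI.1 reserves before any comparison, guided by the Protocol's instruction to compute the index for each subject. The extent of incomplete follow-up will be visible by group under SAP V.3.

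Under the assumed inputs, an arm's mean could be off by 0.25 to 3.0 points with exclusion or 0.1 to 1.5 with recorded-only scoring. The group difference is affected only if the loss, or the kind of subject lost, differs by arm. Neither size nor direction can be derived from the documents, and neither rule is shown to be better. This conclusion depends on loss being low, as the plan expects. Substantial or clearly unequal loss would make the choice matter more, and the planned reporting would reveal it.

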## VI.4 Exploratory analyses

Exploratory analyses will be performed to examine whether age, sex and duration of surgery individually interact with RIC effects on the primary outcome and laboratory outcome parameters. For the primary outcome multivariable regression with interaction terms between a specified variable and RIC will be used. For the laboratory analytes a similar approach with mixed ANOVA will be used.

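### For the repeated plasma analytes, excluding subjects under SAP VI.1 and using mixed ANOVA under V.2 would let one missed postoperative draw discard a subject's other three samples; a likelihood-based repeated-measures model would keep them

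*SAP*

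**What the plan says.** SAP VI.1 (Missing data) gives the rule for endpoints: "Subjects with data missing for a particular outcome would be excluded from that analysis". Its next paragraph makes an exception, by a missing indicator, where "a baseline value of a continuous variable such as the laboratory analytes is missing will be included in the analyses of that outcome". No such exception is made for later values. The same section states: "The number of subjects in whom data would be missing is expected to be low due to the prospective nature of the study". It promises a description of how data are missing, and adds: "Additional decisions about handling missing data would be made prior to any intergroup comparisons are performed".

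Under SAP V.2 the repeated measures of inflammation, acute phase response and complement are to be "analyzed with mixed analyses of variance (ANOVA) to examined for interaction between treatment and time". For the interactions with age, sex and duration of surgery, SAP VI.4 (Exploratory analyses) says: "For the laboratory analytes a similar approach with mixed ANOVA will be used".

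Protocol VII.5 plans four draws: baseline, one hour after skin closure, and one hour after each of the second and third interventions (POD 1 and POD 2).

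SAP III.1 sets the primary efficacy analyses in an intention-to-treat (ITT) population "that would include all randomized subjects". SAP III.2 reserves for secondary analyses a per-protocol population that "would include only subjects that completed all three interventions and follow up".

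**The concern.** The unit that VI.1 removes is the subject, not the sample. A classical mixed ANOVA needs every time point for every subject, so the two provisions together give a complete-case analysis of each analyte. A subject who missed only the POD 2 draw would also lose the baseline, post-closure and POD 1 values already collected.

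This matters for the second of the protocol's two objectives, which tests time-dependent differences between arms in these analytes. Two consequences need to be kept apart. If losses are unrelated to the analyte, information is wasted and power falls. If losses differ by arm and depend on an earlier value, exclusion also distorts time points that were fully collected, and the treatment-by-time test can reject too often when there is no effect.

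The documents make unequal loss conceivable. The last two draws are timed from completed sessions (Protocol VII.5), subjects may stop a session for pain (Protocol X.1), and the postoperative cuff pressure is systolic plus 50 mmHg in the RIC arm against 20 mmHg in the sham arm (Protocol V).

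**Working it through.** **Plan's own figure.** There is none to reproduce. SAP VI.4 (Sample size and power) makes no calculation, and no completion or missing-data rate is given. Every loss rate, sample size and effect below is an assumption.

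**Samples discarded.** Suppose a share m of subjects misses only the POD 2 draw. The average number collected per subject is 4 − m. Each subject with a missed draw loses the other 3. The discarded share of collected samples is 3m/(4 − m):

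- m = 5%: 0.15/3.95 = 3.8%
- m = 10%: 0.30/3.90 = 7.7%
- m = 20%: 0.60/3.80 = 15.8%
- m = 30%: 0.90/3.70 = 24.3%

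**Simulation set-up.** Normal data with SD 1, within-subject correlation 0.5, four time levels, only POD 2 missed, 4,000 replicates per cell (Monte Carlo SE 0.3 to 0.8 percentage points). Complete-case mixed ANOVA, with the interaction tested on F(3, 3(N − 2)), is compared with a REML random-intercept model on all samples. The treatment-by-time test is at 0.05.

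**Power.** Effect of −0.5 SD at POD 1 and POD 2, with equal random loss in both arms:

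| POD 2 loss | 30 per arm: ANOVA | 30 per arm: model | 60 per arm: ANOVA | 60 per arm: model |
|---|---|---|---|---|
| 0% | 61% | 61% | 92% | 92% |
| 10% | 55% | 60% | 89% | 90% |
| 20% | 50% | 58% | 83% | 89% |
| 30% | 44% | 56% | 78% | 89% |

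**False positives for the complete-case ANOVA, with no true effect:**

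- Loss of 10% in both arms: 4.6% to 5.4%.
- Unequal loss unrelated to the analyte, 30 per arm: 5.1% (RIC 30%, sham 10%) and 5.2% (RIC 40%, sham 10%).
- RIC loss rising with the post-closure value (logit slope 1 per SD), but low overall (RIC 10%, sham 5% at random): 4.5% with 30 per arm and 6.1% with 60.
- The same link with RIC loss of 20%, 30% or 40% and sham 10% at random: 5.9%, 6.2%, 8.0% with 30 per arm; 7.0%, 8.2%, 11.6% with 60; 7.8%, 11.3%, 15.3% with 100. The random-intercept model gave 4.6% to 5.4% across these cells.
- The same link in both arms, RIC 30% and sham 10%: 5.3%, 6.1%, 7.5% with 30, 60, 100 per arm.

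**Does the alternative depend on its covariance?** Yes. The random-intercept model above matches the way the data were generated. With correlation decaying at 0.7 per step (RIC 30% linked to the post-closure value, sham 10%; 1,200 replicates, SE about 0.8 points), it gave about 6.9% with 60 per arm and 7.7% with 100. The complete-case ANOVA gave 8.4% and 9.8%. An unstructured covariance gave about 5% to 6%.

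**The case against.** The strongest reply is that the SAP never states the discard rule in so many words. If outcome means a single analyte at a single time, and mixed ANOVA is fitted as a likelihood mixed model, nothing is lost. VI.1 also keeps subjects with a missing baseline, expects few missing data, promises to describe the pattern, and leaves room to decide more before arms are compared. This stands in part: the defect rests on the ordinary reading, not on an explicit instruction. But the SAP does not state the lenient reading, the only rule it gives for later values is exclusion of the subject, and the deferred decisions have no content.

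A reader might infer two stronger claims, and neither is supported.

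The first is that the rule breaches the ITT definition. SAP III.1 ties ITT to the primary efficacy analyses, and the plasma analytes are secondary endpoints. Exclusion does move their analysis towards completers, but it does not directly breach III.1.

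The second is that the analyte results will be biased, or falsely positive in up to 15% of trials. That figure needs 40% loss in the RIC arm, 100 subjects per arm and a link between the post-closure value and missing POD 2. No passage links analyte level to tolerance, and none says that a draw is withheld after a stopped session. Protocol X.1 expects little pain and reports that most subjects in the liver-transplant pilot completed four postoperative sessions, against two here. Unequal loss alone does not inflate the error rate.

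**Conclusion.** The point holds as a cheap improvement to the analysis of secondary endpoints. On the ordinary reading of VI.1 with V.2, each missed POD 1 or POD 2 draw costs three collected samples per analyte. The expected consequence is lost precision: about 50% power against 58% at an assumed 20% random POD 2 loss, 30 per arm and a 0.5 SD effect, and a smaller gap at lower loss. Bias is possible but not shown. It requires loss that is unequal by arm and related to earlier analyte values, and it is negligible at low loss. Its real size and direction cannot be derived from the documents, which give neither a sample size nor a completion rate. The primary CCI analysis is not affected.

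**What to change.** In SAP V.2, VI.1 and the exploratory laboratory analyses, replace mixed ANOVA with subject exclusion by a likelihood-based (REML) repeated-measures model for the plasma analytes:

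- Use every available sample from all randomized subjects.
- Fit treatment, time and treatment-by-time as fixed effects, with baseline as one of the four time levels. Keep treatment-by-time as the omnibus test.
- Use an unstructured within-subject covariance. Fix in advance the fallback structure if it fails to converge and the small-sample degrees-of-freedom method.
- State that the missing-indicator rule for baseline analytes no longer applies to these endpoints, because the model already keeps subjects whose baseline is missing. Otherwise the two rules conflict.
- Report missing samples by arm and time point.

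The cost is SAP wording and standard software, with no added subjects or draws. The drawbacks are that the model assumes missingness is explained by the observed data, and that the covariance structure must be prespecified.

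Optionally, Protocol VII.5 could say whether and when the POD 1 and POD 2 samples are drawn if a session is stopped or not begun. That would help limit missing samples, but the point does not depend on it.
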